1.0 Introduction

1.1 Study Conduct

This study will be conducted in compliance with the protocol approved by the Institutional Review Board, and according to Good Clinical Practice standards. No deviation from the protocol will be implemented without the prior review and approval of the IRB except where it may be necessary to eliminate an immediate hazard to a research subject. In such case, the deviation will be reported to the IRB according to its policies and procedures.

1.2 Background

Despite many advances in imaging and therapy, prostate cancer remains the second most common cause of cancer-related death of men in the United States. The management approach to men diagnosed with low risk prostate cancer remains a socioeconomic dilemma with no clear consensus whether prostatectomy or whole-gland radiation therapy improves outcomes and these treatments are often associated with significant long-term morbidity negatively impacting quality of life parameters that require long-term management. Another approach has been ‘active surveillance’ but often these men are under staged at the time of diagnosis, and will clinically progress and ultimately receive definitive therapy to the whole gland, while more frequently many men opt for partial gland ablative therapy with surveillance.

Previous research has demonstrated the value of radiation dose escalation in patients with prostate cancer (Bolzicco 2010, Friedland 2009). However, to date, most paradigms have focused on dose escalation applied to the whole gland. It is recognized that higher doses to the whole gland are associated with higher treatment related toxicities (impotence, incontinence, rectal fissures) (Zelefsky). Now, with advanced delivery techniques such as intensity modulated radiation therapy (IMRT), proton therapy, and stereotactic body radiation therapy (SBRT) dose escalation can be achieved targeting sub-volumes of the prostate. Preliminary evidence suggests that sub-volume dose escalation based upon molecular and anatomical imaging may improve outcomes (Eggner 2007, Ellis 2010). This research will evaluate the safety and efficacy of SBRT for focal partial gland therapy in prostate cancer.

There is growing concern over the risk of over treating patients who may not be at risk of dying from the disease. Prostate cancer remains the sole malignancy where treatment is always delivered to the whole organ in routine practice. Many low risk patients therefore opt for Active Surveillance rather than immediate whole gland treatment to limit treatment related decrease in quality of life associated with either surgery or whole gland radiation. A growing body of evidence also suggests that treatment of the dominant prostatic lesion/s may be sufficient to prevent systemic disease progression, and that small lesions less than 5 mm may be indolent, thus if left untreated initially may not be likely to progress in a clinically significant manner. Additionally once a dominate lesion is treated, the patient may return to a course of active surveillance using PSA, physical examinations, and repeat MRI or biopsy as clinically indicated (Scardino 2009, Cosset 2013).

Despite early success using molecular and anatomical data to identify sub-volumes of disease for image-guided therapy, physicians remain reticent to escalate dose based upon imaging findings alone, which are inherently limited by sensitivity and specificity (Ellis 2010, Pinto 2011). Therefore, a treatment planning methodology that provided direct 3D spatial correlation of imaging sets with the gold standard of histopathology would be highly effective to exclude normal tissue (false positives by imaging) and simultaneously allow radiation dose escalation to clearly delineated “true positive” target volumes.

By using high resolution 3T MRI imaging with parametric sequencing to identify areas suspicious for harboring malignancy, we believe that focal therapy could be safely delivered to properly selected patients. Biopsy confirmation of the imaging findings for both suspicious and non-suspicious regions based on MRI imaging would be used to confirm that cancer is present at the suspected locations using a patented methodology to define the treatment target volumes. Rather than treating the whole gland, therapy could then be targeted to partial prostate volumes with the goal of reducing treatment related morbidity and long term cost for treatment.

A recent systematic review of the focal therapy in localized prostate cancer evaluated 2350 cases reported in 30 studies through October 2012, mainly delivered in low and intermediate disease, and some high-risk patients where imaging suggested unilateral disease. Post therapy incontinence, and erectile function toxicities were limited, with promising short- to medium term disease free survival outcomes (Valerio 2013). In a separate critical appraisal of focal therapy for localized prostate cancer, Eggner et al. (representing an international multidisciplinary task force with expertise in prostate cancer) evaluated “the focal lesion paradigm” (Eggner 2007) and the role of focal ablative therapy. This review panel concluded with encouragement for prospective clinical research in emergent focal technologies for the treatment of unifocal and biologically unifocal prostate cancer – as needed options for men resistant to active surveillance and watchful waiting. A number of other authors from major universities, have more recently reported good outcomes with whole-gland, unilateral and focal ablative cryotherapy applications. These authors list focal ablative options to include focused ultrasound, brachytherapy, thermotherapy, photodynamic therapy, and stereotactic radiosurgery (Polascik 2008, Hou 2009, Pisters 2010, Boomers 2013). Radiation therapy is uniquely qualified for use in focal therapies as it stands alone as a standard of care for prostate cancer treatment with long term outcomes showing safety and efficacy for whole gland disease control, and growing evidence with partial gland focal therapy (Ellis 2010, Katz 2010, Cossett 2013).

Focal image-guided radiation therapy is a novel alternative that may provide a cost-effective and less morbid treatment option for men diagnosed with low-risk disease. Conceptually, focal therapy targets only diseased prostatic tissue and spares adjacent non-cancerous prostate tissue which may be as efficacious as whole-gland therapy but with less side effects. Further, clinical evidence suggests that the α/β ratio of prostate cancer is quite low providing an opportunity for greater therapeutic gain with hypofractionated courses of radiotherapy compared to traditional fractionated treatment. The hypothesis of this proposal is multiparametric MR data including T2 weighted, contrast enhanced, and diffusion weighted imaging when correlated with marked histopathology biopsy sites confirming tumor foci, will allow appropriate patient selection for focal radiation therapy with a higher sensitivity than routine MR imaging alone. Further, that using advanced imaging to guide dose modulation in focal stereotactic body radiation therapy (SBRT), also named stereotactic ablative radiotherapy, may provide equivalent outcomes to whole-gland therapy with shortened treatment courses and decreased toxicity. This prospective investigational review board (IRB) approved, single institution pilot study will be used to demonstrate clinical feasibility and may potentially lead to future federally funded Phase I/II and consortium supported multi-center clinical research trials for focal SBRT in localized low-risk prostate cancer patients.

Most recently, parametric sequencing MRI have been reported to identify prostatic regions that are highly suspicious for tumor foci (Valerio 2013). The current study will be used to help select for the proper group of patients for whom focal therapy may be appropriately offered. Men who have a diagnosis of localized prostate cancer with only moderately elevated PSA and Gleason score of 7 or lower without either a dominate pattern 4 or a tertiary pattern 5 seen on initial pathology may be

eligible for evaluation, as these patients meet the institutional clinically accepted determination making them eligible for Active Surveillance (AS). Many men meeting AS criteria, however, prefer treatment with curative potential, and opt for partial gland therapy aiming at limiting potential treatment related toxicities that may be associated with treatment to whole gland. A staging 3T MRI is our adopted standard of care evaluation for men presenting for radiation therapy planning with parametric sequences. In the current study we will use the staging and treatment planning images to evaluate regions highly suspicious for tumor foci as a screening tool for appropriateness of focal therapy and for eligible patients, for use in guided biopsy to confirm pathology on the imaging studies.

Standard radiotherapy for the treatment of prostate cancer is delivered at 1.8 to 2 Gy per fraction in a protracted course over 8 to 9 weeks to total doses in the range of 78 to 81 Gy. Following the published work of Hall and Brenner suggesting that prostate cancer may have a lower alpha beta ratio describing the cell line's ability to repair damage caused by ionizing radiation; many centers have routinely adopted into clinical practice that prostate cancer may be treated using larger doses per fraction ranging in size from 3 to 19 Gy in as many as 20 or as few as a single fraction of therapy (Brenner 1999). The assumption is that the alpha beta ratio of most tumors is as high as 10, while the surrounding normal tissues at risk of late radiation reactions is around 3 to 5 (Yoshioka 2013). Positive histopathology findings on co-registered diagnostic MRI data sets (T2 and parametric functional imaging) will be used to segment a dominant biologic target volume and improve disease mapping across the gland. Subjects will then be treated in a series of three SBRT (typically every other day) treatments to deliver a total dose of 29.25 Gy in 9.75 Gy fractions, yielding a total biologic equivalent dose (BED) of 273.15 allowing dose to reach the desired minimal BED of 268 with an assumed alpha beta of 1.2 for prostate cancer as suggested by Martinez (2011). A similar dose regimen has been published by Barkati et.al. using HDR brachytherapy in a three fraction dose escalation trial to deliver minimal dose of 30 Gy in 3 fractions over two days to a maximal dose of 34.5 Gy at 11.5 Gy per fraction. (Barkati 2012). While the published 3 fraction HDR regimen gave a minimal dose of 10 Gy, we feel that 9.75 Gy per fraction is effectively equivalent when taking into account the additional 12 cGy per fraction we will be giving to allow for tracking of intrafraction prostate motion with Image Guided Radiation Therapy using a series of 4 cone beam CT image sessions obtained before, during and after each fraction, thus accounting for a daily fractionated dose of 987 cGy, or 9.9 Gy. What is uniquely novel in this protocol is not the total dose of radiation delivered but rather that it is to be delivered in a non-invasive fashion using SBRT, and more importantly delivered to a novel partial prostate volume using a patented methodology to define the volume at risk to be treated using focal therapy for prostate cancer. This methodology may be adopted as a template for directing therapy to partial organ volumes using other treatment modalities based on the results of this trial if the use of tracked histopathology location is found to have significant influence on the selected treatment volumes in this study beyond what would be used based on functional and anatomic imaging studies alone.

2.0 Study Objectives

Hypothesis: Multiparametric MRI with histopathological correlation can be used to treat sub-volumes of the prostate with focal SBRT in low- and intermediate-risk patients leading to equivalent outcomes as whole-gland therapy with reduced toxicity and improved quality of life.

To validate the above hypothesis in this prospective study, the specific aims include:

- 1) Evaluate the correlation of histopathology findings in comparison to regions of the prostate reported to be suspicious for harboring tumor burden on multiparametric MRI report/s;
- 2) Demonstration of the dosimetric and radiobiological advantages of focal SBRT versus whole-gland radiation therapy;
- 3) Evaluation of clinical outcomes in focal SBRT for localized prostate cancer.

3.0 Study Design

3.1 General Design

This 2-year pilot study will include patients with positive diagnostic prostate biopsy, with or without positive digital rectal exam (clinical stage T2a or T1cN0M0), Gleason score $\leq 7(3+4)$, with a PSA ≤ 10 ng/mL and routine imaging that includes bone scan and MRI of the pelvis.

Patients eligible for either whole-gland therapy or active surveillance will be evaluated by staging MRI and the scan used to screen for disease burden within the gland. Patients identified with a focal dominate lesion greater than 5 mm in size confirmed with imaging and biopsy will be eligible for this trial. Patients found to have no focal abnormalities will be offered other disease management options off study, such as active surveillance or whole gland therapy with traditional fractionated external beam radiation therapy (EBRT) and/or brachytherapy.

Eligible patients (≤ 6 total per year) will sign consent to enroll and be treated with focal SBRT on study at a dose of 29.25 Gy in 3 fractions (9.75 Gy per fraction) to involved sub-volume of the prostate using volumetric modulated arc therapy (VMAT) with the Synergy BMX2 with Agility collimator (Elekta, Stockholm, Sweden and Atlanta, GA).

4.0 Subject Selection and Withdrawal

4.1 General Characteristics of the Proposed Subject Population

Histologically confirmed diagnosis of adenocarcinoma of the prostate. Gleason scores $\leq 7(3+4)$; Clinical stage T1-2a; PSA ≤ 10 ng/mL (PSA should not be obtained within 10 days after prostate biopsy).

4.2 Anticipated Number of Research Subjects

24 screened and 12 enrolled over 2 years.

4.3 Inclusion Criteria

Patients with positive diagnostic prostate biopsy with or without positive digital rectal exam (DRE) (clinical stage \leq T1-T2a or T1cN0M0), Gleason score $\leq 7(3+4)$, with a PSA ≤ 10 ng/mL and routine staging work-up consistent with a diagnosis of localized prostate cancer. Patients eligible for either whole-gland therapy or active surveillance will use the staging MRI to screen for intraprostatic disease burden. Patients having a single focal dominate lesions greater than 5 mm in size confirmed with imaging and biopsy will be eligible for this trial. Patients (≤ 6 total per year) will be treated with focal SBRT delivering on study to 29.25 Gy in 3 fractions (9.75 Gy per fraction) to involved sub-volume. Eligible patients must be able to undergo an MRI with contrast.

Patient's Name _____

Medical Record # _____

Research Nurse /
Study Coordinator Signature: _____ Date _____

Treating Physician [Print] _____

Treating Physician Signature: _____ Date _____

Patients must meet all of the following inclusion criteria to be eligible for enrollment:

- ____ 4.3.1 Patients must have a histologically confirmed diagnosis of adenocarcinoma of the prostate.
- ____ 4.3.2 Patient must have a history/physical examination with digital rectal examination of the prostate within 90 days prior to screening
- ____ 4.3.3 Age ≥ 18 years. Because no dosing or adverse event data are currently available on the use of the study treatment in patients <18 years of age, children are excluded from this study.
- ____ 4.3.4 ECOG Performance status must be level 0 or 1 within 60 days prior to registration [See Appendix A].

ECOG PS = _____
Date: _____

- ____ 4.3.5 Patient must have a histological evaluation of the prostate biopsy with assignment of a Gleason score to the biopsy material; Gleason scores $\leq 7(3+4)$
- ____ 4.3.6 Patients must have adequate renal function as defined below:

Serum Creatinine $<$ or $=$ 1.5 times the ULN (Normal: ≤ 1.17 mL/min/1.73 m²)
Serum Creatinine: _____
Date of Test: _____

- ____ 4.3.7 Clinical stage a $</=$ T1-T2a (AJCC 7th edition)
- ____ 4.3.8 PSA ≤ 10 ng/mL within 90 days prior to registration. PSA should not be obtained within 10 days after prostate biopsy.
- ____ 4.3.9 Subjects must have the ability to understand and the willingness to sign a written informed consent document.
- ____ 4.3.10 Patient willing and able to complete the Expanded Prostate Cancer Index

Composite (EPIC) questionnaire (Baseline, 6, 12 and 24 months post end of radiation therapy)

- _____ 4.3.11 Patients must be able to undergo an MRI with contrast
- _____ 4.3.12 Bone scan, when clinically indicated, completed within 90 days

4.4. Exclusion Criteria

The presence of any of the following will exclude a patient from study enrollment.

- _____ 4.4.1 Evidence of distant metastases
- _____ 4.4.2 Regional lymph node involvement
- _____ 4.4.3 Previous radical surgery (prostatectomy), cryosurgery, or HIFU for prostate cancer
- _____ 4.4.4 Previous pelvic irradiation, prostate brachytherapy, or bilateral orchiectomy
- _____ 4.4.5 Previous hormonal therapy, such as LHRH agonists (e.g., goserelin, leuprolide) or LHRH antagonists (e.g., degarelix), anti-androgens (e.g., flutamide, bicalutamide), estrogens (e.g., DES), or surgical castration (orchectomy)
- _____ 4.4.6 Use of finasteride within 30 days prior to registration. PSA should not be obtained prior to 30 days after stopping finasteride.
- _____ 4.4.7 Use of dutasteride within 90 days prior to registration. PSA should not be obtained prior to 90 days after stopping dutasteride.
- _____ 4.4.8 Previous or concurrent cytotoxic chemotherapy for prostate cancer
- _____ 4.4.9 Severe, active co-morbidity, defined as follows:
 - _____ 4.4.10 Unstable angina and/or congestive heart failure requiring hospitalization within the last 6 months
 - _____ 4.4.11 Transmural myocardial infarction within the last 6 months
 - _____ 4.4.12 Acute bacterial or fungal infection requiring intravenous antibiotics at the time of registration
 - _____ 4.4.13 Chronic obstructive pulmonary disease exacerbation or other respiratory illness requiring hospitalization or precluding study therapy at the time of registration
 - _____ 4.4.14 Hepatic insufficiency resulting in clinical jaundice and/or coagulation defects; note, however, that laboratory tests for liver function and coagulation parameters are not required for entry into this protocol. (Patients on Coumadin or other blood thinning agents are eligible for this study).

4.4.15 Acquired Immune Deficiency Syndrome (AIDS) based upon current CDC definition; note, however, that HIV testing is not required for entry into this protocol. The need to exclude patients with AIDS from this protocol is necessary because the treatments involved in this protocol may be significantly immunosuppressive. Protocol-specific requirements may also exclude immuno-compromised patients

4.4.16 Patients unable to undergo an MRI with contrast.

4.5 Subject Recruitment and Screening

Subjects will be recruited from patients presenting to Urology and/or Radiation Oncology for consultation with a diagnosis of localized prostate cancer.

4.6 Inclusion of Women and Minorities

Men and members of all races and ethnic groups are eligible for this trial. Women will not be eligible for this trial.

5.0 Registration

All subjects who have been consented are to be registered in the OnCore Database. For those subjects who are consented, but not enrolled, the reason for exclusion must be recorded.

All subjects will be registered through a study coordinator and will be provided a study number by calling [contact]

5.1 Early Withdrawal of Subjects

Criteria for Removal from Study

Subjects may be removed from the study upon request or at the discretion of the Principal Investigator for safety reasons, failure of subject to adhere to protocol requirements, subject consent withdrawal, or disease progression. Withdrawn subjects may be replaced.

Follow-up for Withdrawn Subjects

Subjects may withdraw from the study at any point. If subjects withdraw prior to delivery of SBRT, they may be replaced with an additional subject(s). Follow up for withdrawn subjects will continue per standard of care for disease stage as reported through the staging biopsy, off study. All routine standard of care imaging and physical exams to monitor disease progression, may be conducted as similar to that care described on trial. Data collected following consent and registration through the screening biopsy will be reported for all subjects, including those withdrawn prior to SBRT.

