All clinically relevant radiologic images will be transferred to the Radiation Oncology Pinnacle (Philips, Cleveland, OH) treatment-planning system. Using the various MRI sequences and the CT image data sets, a composite gross tumor volume (GTV) will be generated. The focal GTV will be contoured and approved by the attending radiation oncologist and urologist. The 4D CT will be fused with the treatment planning CT and an internal target volume (ITV) will be generated. The location of tumor foci from each positive biopsy core will also be segmented and expanded by 5mm to add to the PTV along with imaging data sets. An additional 0.3-0.5 cm margin will be placed around the image data set ITV to generate a final PTV to account for set-up variation. The use of abdominal compression may be used to decrease the volume of ITV since there is no real-time target tracking. Surrounding normal structures, including the rectum, small bowel, bladder, femora, seminal vesicles, penile bulb, and skin will be contoured. Skin is defined as a 0.5 cm concentric ring beneath the skin.

Mid Treatment and Post SBRT (MRI) with multiparametric sequences (mpMRI)

Each subject will be offered up to 4 additional MRI scans: 1 during therapy (between the 2nd and 3rd fractionated treatments), at 6 months following the end of radiation therapy, and again at 12 and 24 months. All mpMRI will be requisitioned in the same manner as described above (Staging MRI) as described above at page 16 (6.1 Imaging the Prostate), with the exception that contrast with gadolinium is preferred. If patients are unwilling or clinically unable to undergo contrast or have all follow-up MRI scans, the patient will remain on study and followed for PSA response and toxicity outcomes.

Computed Tomography (CT)

CT will be fused with MRI scans and used as a primary image platform for treatment planning. It is preferred that CT with contrast be acquired, unless clinically contraindicated. The simulation should be performed in the supine treatment position, in the custom made immobilization device, with the fiducial markers and rectal balloon in place (where utilized). Axial cuts of 2.0 mm or less will be acquired throughout the pelvis and prostate from the top of the iliac crests superiorly to the perineum inferiorly.

Contrast

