7.2 Study Visits

Biopsy and Fiducial Placement – visit #2

- Weight
- Vitals including blood pressure, pulse, respiratory rate, temperature
- Physical examination
- Guided biopsy
- Fiducial placement

MRI and CT scans for RT SIM – visit #3

- RT CT (with contrast unless contraindicated) for simulation
- Pelvic MRI with Contrast
- Pelvic CT for SIM

SBRT #1 – visit #4

- RT treatment

SBRT #2 – visit #5

- RT treatment

MRI – visit #6

- Pelvic mpMRI with Contrast

SBRT #3 – visit #7

- Adverse events assessment (may be completed by telephone call within 7 days post visit 7)
- RT treatment

Follow up, every 3 months for up to 24 months – visits #8 - #16

- Weight
- Vitals including blood pressure, pulse, respiratory rate, temperature
- Physical examination
- ECOG performance status
- Quality of life Score standard of care IPSS and SHIM Scores
- Adverse events assessment

Post SBRT Follow up Measurements

- PSA to be completed at ALL follow up visits

- DRE to be completed at **ALL** follow up visits
- Serum Creatinine and BUN Blood Draw at **6, 12, and 24** months follow up prior to MRI
- Pelvic MRI to be completed at **6, 12, and 24** month follow up visits with contrast
- EPIC EQ D5, Sexual Medication/Device screening to be completed at **6, 12 and 24** months

Any positive results for staging Post RT (positive digital rectal exam or evidence of biochemical failure using the clinical nadir +2 definition (serum PSA rise above 2ng/mL from the post therapy nadir (Phoenix, Abramowitz 2007) may trigger clinical indication for SOC staging MRI to rule out disease progression. If acquired, this data will be collected for comparison to other serial MRI data. Should a patient be deemed to have failed therapy using the Phoenix criteria (nadir +2ng/mL PSA) the subject/s will be referred for consultation for review of options for salvage therapy, and if the patient elects a second treatment the subject will be taken off study.

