9.0 Safety and Effectiveness Assessments

The primary goal of this pilot study is to determine if MRI with multiparametric sequences mpMRI can be used as a mapping tool for correlation with histopathology results, providing a more informed method for the delivery of focal hypofractionation treatments. Hypofractionated radiation using SBRT is a promising tool for delivery with intent to cure. The use of focal partial prostate SBRT should show lower toxicity, and will be evaluated for equivalent efficacy. A co-primary end point of the pilot study will be to show that patients maintain acceptable HRQOL status as compared to baseline. There will be two co-primary endpoints based on summary scores from the bowel and urinary domains of the EPIC questionnaire. Although HRQOL is collected at multiple time points, it has been decided that EPIC, EQ D5 and Sexual Medication/Device Screening data collected at 6, 12 and 24 months post therapy will be compared to baseline to test the primary hypothesis. The percentage of patients with change in EPIC bowel domain score (baseline to 1-year) that was worse than 5 points and a change in EPIC urinary domain score that was worse than 2 points are felt to be clinically meaningful endpoints to assess for tolerability and safety. A rate for the worse-than-5 point change in bowel score of up to 35% of patients will be considered acceptable, with a rate $\geq 55\%$ specified as unacceptable. Similarly, a rate for the worse-than-2 point change in urinary score of up to 40% will be considered acceptable, with a rate $\geq 60\%$ unacceptable. The PSA results along with serial MRI assessments will be used to test the hypothesis of equivalent disease control compared to historical data for whole gland therapy using SBRT. Standard of care quality of life assessments International Prostate Symptom Score (IPSS) and sexual health inventory for men (SHIM) scores will be acquired as part of the standard care prior to and following SBRT. When collected, this data will be collected and reported.

Analysis of the Primary Endpoints

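### As worded, Section 5.1 lets a treated man removed for safety or progression be replaced and followed off study, so his later adverse events and 1-year EPIC may go uncollected

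*Combined protocol and SAP*

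**What the plan says.** **Replacement.** The removal paragraph of Section 5.1 allows removal at the investigator's discretion for safety or non-adherence, and ends "subject consent withdrawal, or disease progression. Withdrawn subjects may be replaced". The follow-up paragraph opens with "Subjects may withdraw from the study at any point" and continues "If subjects withdraw prior to delivery of SBRT, they may be replaced with an additional subject(s". It then adds "Follow up for withdrawn subjects will continue per standard of care for disease stage as reported through the staging biopsy, off study". Its promise to report data from all subjects covers only data through the screening biopsy.

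**Ways of leaving or staying.** Under Section 7.2, a PSA failure leads to referral, and "if the patient elects a second treatment the subject will be taken off study". In contrast, a man who declines contrast or some follow-up MRI scans stays in: "the patient will remain on study and followed for PSA response and toxicity outcomes" (Section 6.1.1).

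**Endpoints exposed to later loss.** Section 9.0 defines a co-primary measure as "The percentage of patients with change in EPIC bowel domain score (baseline to 1-year) that was worse than 5 points", acceptable up to 35% and unacceptable from 55%. For the urinary domain, "a rate for the worse-than-2 point change in urinary score of up to 40% will be considered acceptable", and 60% or more is unacceptable. Section 9.1 defines late toxicity as beginning more than 180 days after radiotherapy, and Section 10.2 promises proportions with 95% intervals.

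**Nearby rules.** Section 9.2 sets an evaluable set for acute toxicity within 90 days. Section 9.1 admits to the HRQOL analysis anyone with a baseline and one later form, and substitutes the last available value for a missing 24-month value. Section 10.2 assumes data missing at random in its mixed models of the scores. Section 12.3 retains data up to withdrawal. The instruction boxes on two forms in Appendix 3 require quality-of-life questionnaires at every time point.

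**The concern.** Progression is a study outcome, and a safety removal is tied to the toxicity result. A rule that allows men to be replaced for those reasons after treatment makes membership of the final group depend on how they fared. If their later follow-up also moves off study, the men most likely to show late toxicity or a worse 1-year EPIC are those most likely to be missing. Late toxicity and both EPIC percentages would then look better than they were, and data never collected cannot be recovered at analysis.

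Section 10.2 describes the study as a source of preliminary data for later studies, and Section 19.0 plans a publication on late toxicity. Those uses are what would suffer.

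**Working it through.** **1. Which texts reach a treated man who is removed?**

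- *Section 5.1, removal paragraph:* he may be replaced.
- *Section 5.1, follow-up paragraph:* replacement is mentioned only before SBRT. Its phrase about an additional subject settles the pre-SBRT case but does not say how a replaced treated man is counted.
- *Section 12.3:* his data up to withdrawal are used. Collection is not extended.
- *Section 9.2:* he is evaluable for acute toxicity. No counterpart is stated for late toxicity.
- *Section 9.1, HRQOL:* if removed between 6 and 12 months, his baseline and 6-month forms put him in the set, but he has no 1-year score. The last-value rule is written for the 24-month change and the missing-at-random assumption for the mixed models, so neither settles the 1-year percentage.
- *Appendix 3 instructions:* they accept only death or documented refusal as grounds for omitting questionnaires. They head the Sexual Medications/Devices and EQ-5D forms, do not mention men taken off study, and do not cover adverse events.

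**2. How likely is at least one removal?** The documents give no rate, so r per treated patient is an assumption. P(at least one of 12) = 1 − (1 − r)^12.

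| Assumed r | P(at least one removal) |
|---|---|
| 5% | 46% |
| 10% | 72% |
| 20% | 93% |

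**3. Effect on the EPIC percentages.** Suppose one treated man is unscored at 1 year and had in fact worsened. Reported rate = k/n among men scored; rate with full follow-up = (k+1)/(n+1). Take n = 11 (12 treated, one unscored, not replaced) and n = 12 (13 treated, one replaced). Every k was compared with the Section 9.0 limits. The reading changes at four counts (exact Clopper-Pearson 95% intervals):

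| Domain | Reported | With him followed | Limit crossed |
|---|---|---|---|
| Bowel | 6/11 = 54.5% (23.4 to 83.3) | 7/12 = 58.3% (27.7 to 84.8) | 55% |
| Bowel | 4/12 = 33.3% (9.9 to 65.1) | 5/13 = 38.5% (13.9 to 68.4) | 35% |
| Urinary | 4/11 = 36.4% (10.9 to 69.2) | 5/12 = 41.7% (15.2 to 72.3) | 40% |
| Urinary | 7/12 = 58.3% (27.7 to 84.8) | 8/13 = 61.5% (31.6 to 86.1) | 60% |

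Each crossing is into or out of the zone between the two limits. None goes from acceptable to unacceptable.

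**4. Effect on late toxicity.** If a removed and replaced man has a late event off study, the report is 0/12 (0 to 26.5%). With follow-up it would have been 1/13 = 7.7% (0.2 to 36.0%).

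**The case against.** The strongest reply is that Section 5.1 is only loosely worded. Sections 3.1 and 4.3 cap treatment at 6 patients per year in a 2-year study, and Section 4.2 anticipates 12 enrolled. Since 2 × 6 = 12, a 13th treated man would need longer accrual or a breach of the cap, whereas replacing an untreated subject fits. On that view the pre-SBRT sentence explains the general one. This is fair, and it is why a reader who infers that 5.1 contradicts itself goes too far: both sentences are permissive and can be read together. But the 12 is headed as an anticipated number, and the cap does not say which sentence governs a treated man. Off-study follow-up is also a problem without any replacement, as the 11-versus-12 rows show.

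A reader might also infer that a removed man's toxicity is lost altogether. It is not: Section 12.3 keeps what was recorded, so a late event that itself prompts removal is retained, and Section 9.1 commits to collecting late Grade 3+ toxicity. Only events after removal are at risk. Nor is it right that no text requires later questionnaires, since the Appendix 3 instructions do so in general terms; they simply do not address men taken off study.

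Finally, limits can also be crossed by holding the count fixed and enlarging the denominator, for example bowel 4/11 = 36.4% against 4/12 = 33.3%. That treats the unscored man as not worsened, a convention the documents do not propose, and it moves the rate opposite to the bias at issue. It is not evidence for this point.

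**Conclusion.** The point holds in a limited form. As written, Section 5.1 permits outcome-dependent replacement of treated men and sends their later follow-up off study, and no other text closes that gap for late adverse events or the 1-year EPIC percentages.

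The size is modest. It rests on an assumed removal of one man who did badly, shifts the reading only at the four counts shown, and is small beside intervals roughly 54 to 60 percentage points wide. Section 9.0 attaches no action to its limits and Section 10.2 disclaims power, so what is affected is how the pilot is read and carried forward. A reader might infer that one missing man could turn an unacceptable result into an acceptable one; the figures do not show that. The unstated late-toxicity set and 1-year denominator would, taken alone, be mainly missing detail. They matter here because the removal rule determines who is missing. This should be corrected, but it does not undermine the study.

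**What to change.** - Reconcile the two sentences in Section 5.1 so that replacement applies only to subjects who withdraw before SBRT.
- Keep every treated patient in the late-toxicity and EPIC sets.
- Continue collecting adverse events and EPIC after removal unless consent is withdrawn, and flag data obtained after a second treatment.
- Report the 1-year EPIC percentages with the numbers treated, scored and missing. Section 9.1 already plans to describe collection patterns.
- Add a sensitivity analysis that counts missing 1-year scores as worsened.

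The cost is a one-paragraph amendment to Section 5.1 and a couple of sentences in Section 9.1 or 10.2, plus the effort of following removed men. Fewer than 12 men may have complete data, and the sensitivity figure is conservative: it will overstate the EPIC rates if some of the missing men had not worsened. No dose or clinical rule changes.
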